3. OVERALL STUDY DESIGN AND PLAN

3.1. Overview

This is a multi-center trial, to be conducted at up to 30 sites in the United States, Canada, and Europe.

Inclusion criteria for participation in the trial include the presence of documented diabetes (Type I or II) with non-healing, full-thickness, University of Texas Classification of Diabetic Foot Ulcers Grade 1 and 2 diabetic foot ulcers of at least 4 weeks duration, but not greater than 1 year, measuring 1cm² or greater and less than or equal to 20 cm².

Subjects will be asked to sign a written informed consent form, approved by an IRB/Ethics Committee, prior to participation in the trial at the screening study visit. Each subject will be assigned a Subject Identification Number, which will be used for identification purposes in order to ensure subject confidentiality. All subject data held on the study Sponsor's database will be anonymised and identifiable only by Subject Identification Number.

Those who continue to meet all of the eligibility criteria after the 2 week run-in period will be enrolled into the trial and randomized to one of two treatment arms: TWO₂ therapy or, Control therapy.

In this trial a maximum of 220 subjects will be recruited. A Group Sequential Designs (GSD) with interims analyses after one third and two third recruited subjects has been chosen that will allow the trial to be stopped if TWO₂ therapy is obviously better than control therapy.

Subjects will be recruited as outpatients in participating wound care centers and clinics. At the screening visit the informed consent document must be signed, the wound will be measured and the subject will receive a standardized off-loading device for weight bearing wounds. The subject will from then on, be treated with predefined dressings used in the total treatment phase of the study.

A diary card will be given to every subject. Subjects will be instructed on keeping the simple diary card to record the use of the TWO₂ or control device, dressing changes and to collect data for health economic analysis. A study ID card will also function as an alert to other providers of participation in a clinical study (example Appendix I).

After a run-in period of 2 weeks the subject will be randomized into the study if the wound-size reduction is less than 30% of the initial measurement and all other inclusion and exclusion criteria are met.

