8. TRIAL CONDUCT

8.1.1. Overview of Screening Treatment and Follow-Up Requirements

Procedure / Examination	Screening & Start Run-In	Baseline * (2 weeks later)	1	2	3	4	5	6	7	8	9	10	11	12	12 wks Follow up	38 wks Follow up
Informed Consent	X															
In-& Exclusion criteria	X	X														
Randomization		X														
Adverse Effects and Events		X	X	X	X	X	X	X	X	X	X	X	X	X	X	X
Medical History/ Preexisting Conditions	X															
Record Concomitant Medications	X	X	X	X	X	X	X	X	X	X	X	X	X	X	X	X
Compliance assessment (treatment, dressings)		X	X	X	X	X	X	X	X	X	X	X	X	X		
Height and Weight	X															
Wound History (Duration; course of healing last 12 months and previous treatment modalities)		X														
Dressing removal / wound cleansing and re-dressing	X	X	X	X	X	X	X	X	X	X	X	X	X	X		
Wound assessment and measurement (location, size)**	X	X	X	X	X	X	X	X	X	X	X	X	X	X		
Pain assessment	X	X	X	X	X	X	X	X	X	X	X	X	X	X	X	X
Neuropathic assessment	X															
Infection Assessment	X	X	X	X	X	X	X	X	X	X	X	X	X	X		
ABI and Secondary Vascular Assessment ***	X															
Dig. Photographs (post debridement)	X	X	X	X	X	X	X	X	X	X	X	X	X	X	X	X
Debridement if needed		X	X	X	X	X	X	X	X	X	X	X	X	X		
Cardiff Wound Impact Schedule ****	X	X													X	X
Lab tests	X														X	
Punch biopsies *****		X				X										
Education on diabetic foot care/off-loading*****	X	X	X	X	X	X	X	X	X	X	X	X	X	X	X	X
Economic assessment		X				X				X				X	X	X
Device competency assessment		X				X				X						

Note: *Baseline visit window is -1/+2 days. All follow-up visit windows are +/- 2 days. 12 and 38 Week follow-up +/- 2 weeks

** Measurement recorded from central assessor report plus manual measurement at baseline

*** Secondary vascular testing only needed if not within 4 months of screening date

**** Cardiff Wound Impact Schedule (debriefing of subjects week 38 Follow up where not previously validated)

***** Optional (none for sub-study)

***** Off-loading with study boot or CROW boot where required

***** Health Economic Assessment (EQ-5D, dressing history up to 8 weeks and significant related medical events)

8.1.2. **Wound Closure Assessment**

Procedure / Examination	Wound Closure Visit # 1	Wound Closure Visit # 2
Verify Informed Consent	X	X
Adverse Events	X	X
Record Concomitant Medications	X	X
Compliance assessment (treatment, dressings)	X	X
Confirm Wound Closure Assessment	X	X
Dressing removal / wound cleansing and re-dressing	X	
Pain assessment	X	X

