Dig. Photographs (post Debridement if needed)	X	X
Debridement if needed	X	X
Cardiff Wound Impact Schedule (If at week 12 on treatment or last visit before follow up)	X	X
Education on diabetic foot care/off-loading Study dressings	X	
Education on diabetic foot care/off-loading Standard of care dressings per PI/Sub I		X
Economic assessment (if week 4, 8 or 12 on treatment or last visit before follow up)	X	X

Note:

* The wound closure visits may occur within the 12 week follow up period

* Visit window is +/- 2 days.

8.2. **Assessment by Time Point**

8.2.1. **Screening Assessment**

Potential subjects should sign a written IRB/Ethics Committee approved informed consent. Inclusion criteria and exclusion criteria are checked. The index ulcer is chosen as the largest ulcer (in surface area) on the foot. The wound has to be measured and assessed. The vascular assessment is performed, and blood taken for the lab tests. Previous treatment modalities for the index ulcer attempted are documented.

If the subject meets all criteria for inclusion into the study the 2 week run-in period is initiated.

The following assessments will be done:

- 1) Obtain informed consent
- 2) Complete subject contact information and demographics
- 3) Assign subject a screening ID number
- 4) Verify subject eligibility by checking against inclusion/exclusion criteria
- 5) Quality of Life Assessment using CWIS
- 6) Medical history
- 7) Concomitant medication
- 8) Height and Weight
- 9) Tobacco use
- 10) Identify index ulcer
- 11) Wound History
- 12) Wound assessment: Location, size and appearance
- 13) Pain assessment of wound using the Visual Numerical Rating Scale
- 14) Neuropathic assessment
- 15) Infection assessment
- 16) Digital Photograph (post debridement)
- 17) Debridement if needed
- 18) Dress wound with study dressings
- 19) Vascular assessment (ABI and toe pressure or tissue pressure or TcPO2 or duplex (below knee))
- 20) Record lab data or blood sample taken to obtain values for:
 - Electrolytes
 - Creatinine

- HbA1c, blood glucose
- WBC
- Albumin and pre-albumin (where routinely available)
- CBC
- C-reactive protein

21) Provide and educate on off-loading boot/CROW boot, study dressings and diary card and ID card

22) Educate on diabetes management and foot care

23) Urine pregnancy for women of childbearing potential

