9.4 Secondary outcome analyses

9.4.1 Time to complete wound closure

The analysis will use the Cox proportional hazards model to determine time to event (healing). Subjects who withdraw from treatment will be entered into the analysis and censored at the time they withdraw from the trial or are lost to follow up. The analysis will consider covariates that might influence the outcome in the trial. Factors considered potentially important in predicting the outcome of treatment will be tested in a Cox model. Stepwise elimination of non significant covariates will be undertaken and only those covariates that remain statistically significant will be retained in the model. Tests of proportionality will be undertaken using graphical (Nelson Aalen) and quantitative methods (Schoenfeld test). The data will be presented graphically using Kaplan Meier graphs. The

results of the multivariable analysis will be presented as Hazard ratios together with 95% confidence intervals and p-values generated from the model.

9.4.2 *Change in wound size*

An important secondary outcome measure is partial wound healing, which is a function of wound area and perimeter change. Care must be taken to choose an appropriate measure for this outcome, as measures such as reduction in area or percentage reduction in area usually lead to biased comparisons. It is proposed that the trial uses the linear healing measure of Gowland-Hopkins & Jamieson⁴⁴ and described in Gilman⁴⁵. This measure is defined as:

$$d = \Delta A/p_{avg}$$

where ΔA is the change in wound area between two successive visits and p_{avg} is the average of the wound perimeters measured at these two visits. 'd' will be calculated weekly after randomization to treatment.

Comparisons of the two treatment groups will be carried out in terms of d, at each of these assessments. An unpaired t test will be carried out at each assessment, to test the hypothesis that the treatment groups do not differ in terms of d, against the alternative hypothesis that the treatment groups differ in terms of d. A 95% confidence interval for the difference between treatment groups in terms of 'd' will be calculated, based on the t test results.

9.4.3 *Wound recurrence rate.*

The wound recurrence rates will be analyzed with a time to event strategy as in 9.4.1.

9.4.4 *Incidence of amputation*

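### Section 9.4.2 compares wound-edge advance (d) between arms by an unadjusted t test, though a pre-randomization value could be formed from run-in photographs; precision is probably lost.

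*Combined protocol and SAP*

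**What the plan says.** Section 9.4.2 gives this outcome some weight: "An important secondary outcome measure is partial wound healing, which is a function of wound area and perimeter change". It warns against raw or percentage area reduction and adopts d, the area change between two successive visits divided by the average of the two perimeters. It says that d "will be calculated weekly after randomization to treatment". For the comparison, "An unpaired t test will be carried out at each assessment", and the 95% confidence interval for the difference "will be calculated, based on the t test results". No covariate is named. By contrast, section 9.3 considers ulcer duration and size, among others, for closure, and section 9.4.1 allows covariates in the Cox model.

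The schedule in section 8.1.1 marks wound measurement and digital photographs at both screening and baseline, with measurements taken from the central assessor's report. Sections 8.2.1 and 8.2.2 both list "Wound assessment: Location, size and appearance" and a post-debridement photograph. Sections 3.1 and 4.1 make randomization conditional on a reduction of less than 30% over the two-week run-in, so the change in size across those visits has to be worked out for each candidate. Section 7.1.1 names circumference only at the baseline assessment.

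**The concern.** Ulcers differ in how fast they close for reasons unrelated to treatment. The run-in is a two-week observation of that speed in each ulcer, under study dressings and, where required, off-loading, before any device is applied. The plan uses it to decide eligibility and then leaves it out of the analysis of a closely related quantity. Whatever part of the between-ulcer variation the run-in could explain stays in the error term, along with whatever baseline area could explain.

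At stake is the width of the interval for the difference in d, and hence the chance of showing a real effect on partial healing.

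**Working it through.** **The plan's own figure.** The documents give a sample size only for closure: 43% against 64%, 80% power, no continuity correction (section 9.1). With the pooled-variance formula:

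- n = [z(alpha/2) x sqrt(2 x 0.535 x 0.465) + 0.8416 x sqrt(0.43 x 0.57 + 0.64 x 0.36)]^2 / 0.21^2
- Two-sided alpha 0.05: (1.960 x 0.7054 + 0.8416 x 0.6896)^2 / 0.0441 = 87.4, so 88 per arm, as stated.
- Alpha 0.022 per look: (2.290 x 0.7054 + 0.8416 x 0.6896)^2 / 0.0441 = 109.3, so 110 per arm, as stated.

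No SD, effect size or power is given for d. The rest of this check is therefore on a relative scale.

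**Reference effect for d.** With 110 per arm and two-sided 0.05, the t test has 80% power for (1.960 + 0.8416) x sqrt(2/110) = 0.378 SD. This assumes that all 220 subjects contribute a value.

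**Effect of adjustment.** Let rho be the correlation between run-in d and on-treatment d among randomized subjects. Adjustment multiplies the residual variance by 1 - rho^2 and the interval width by sqrt(1 - rho^2). Power for the same effect becomes Phi(2.8016 / sqrt(1 - rho^2) - 1.960).

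| Assumed rho | Residual variance | Interval narrower by | Adjusted power |
|---|---|---|---|
| 0.2 | 0.96 | 2.0% | 81.6% |
| 0.3 | 0.91 | 4.6% | 83.6% |
| 0.4 | 0.84 | 8.3% | 86.4% |
| 0.5 | 0.75 | 13.4% | 89.9% |

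At rho 0.5, 110 per arm act like 110 / 0.75 = 147 per arm under the t test.

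**Simulation check.** With 110 per arm and 5,000 trials per setting, t-test and adjusted power were 79.1% and 82.7% at rho 0.3, and 79.1% and 89.7% at rho 0.5. Mean standard errors were 0.135 against 0.129, and 0.135 against 0.117. Type I error lay between 4.7% and 5.4% for both methods.

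**Effect of the run-in rule.** Excluding the fastest run-in healers narrows the range of run-in d and weakens its correlation with later d. To gauge this, the upper 10% to 40% of a normally distributed run-in d was removed. The share is an assumption, and cutting on d only approximates a rule set on percentage area reduction.

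| rho before selection | rho after selection | Variance saved | Adjusted power |
|---|---|---|---|
| 0.3 | 0.26 to 0.20 | 7% to 4% | 82.7% to 81.6% |
| 0.5 | 0.44 to 0.35 | 19% to 12% | 87.7% to 84.9% |

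The power column puts the post-selection rho into the formula above.

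**Can run-in d be formed?** It needs area and perimeter at screening and baseline. Area is measured at both. Perimeter is named only at baseline, but d also needs perimeter at every weekly visit, so it must be read from the photographs there too. The screening photograph can be read the same way. Run-in d spans two weeks and on-treatment d one. With a baseline window of -1/+2 days, the run-in lasts 13 to 16 days, so dividing by its length in weeks is nearly a constant rescaling and barely affects the estimated arm difference.

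**The case against.** The strongest reply is that nothing here is an error. Under randomization the unpaired t test is valid and holds its size. This stands. A reader might infer that omitting baseline healing speed biases the comparison, or that a chance imbalance is a separate harm. The documents do not support either: the t interval already allows for chance imbalance, so that is the same loss of precision described another way.

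The second reply is that the gain is unknown and may be small. This also stands. No value of rho can be taken from the documents. Besides the eligibility rule, the run-in begins with new dressings and off-loading, and debridement around the two measurements may itself alter area. Both could add noise to run-in d, though this is inference.

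Third, a reader might take it that run-in d already exists in the data for everyone. It does not: screening perimeter is not listed as a recorded item, so the value is obtainable but not planned.

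Fourth, filling in a missing run-in value would conflict with section 9.5, which rules out imputation and drops subjects with missing data. That is correct, and section 9.5 must be changed alongside 9.4.2.

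Last, section 9.4.2 has other weaknesses that may matter more. It tests d separately at up to 12 weekly visits with no visit designated. Once an ulcer has closed at two successive visits, d is zero divided by zero. Adjustment cures neither.

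**Conclusion.** The point holds as a modest loss of efficiency on one secondary outcome. Section 9.4.2 uses a valid but unadjusted comparison where a pre-randomization value of the same measure can be derived and baseline area is on record.

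For an effect that the t test would detect with 80% power, adjusting for run-in d adds about 2 points at rho 0.2 and about 10 at rho 0.5. The run-in rule makes the lower part of that range more likely. These figures rest on an assumed rho, a linear relation, and all 220 subjects contributing. Any extra gain from baseline area is not quantified.

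The stronger reading, that the wound-size analysis is biased or that the trial's main conclusion is at risk, is not supported. The closure endpoint, its analysis and the total of 220 do not depend on this choice. It is a worthwhile improvement, not a necessary correction.

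**What to change.** In section 9.4.2:

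- Replace the unpaired t test with a linear model of d on randomized arm, adjusted for run-in d (screening to baseline, per week) and log baseline area. Specify both covariates in advance and keep them regardless of significance.
- Report the adjusted difference with its 95% confidence interval, and keep the unadjusted t test as a supplement.
- State that area and perimeter are read from the screening photograph in the same way as for the weekly visits.

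In section 9.5, add an exception confined to a missing baseline covariate: use the overall mean of run-in d, calculated without regard to arm, so that no randomized subject is dropped for an unreadable screening image. Outcome data stay under the existing rule.

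The cost is SAP wording, one further reading of a photograph already taken, and two degrees of freedom (218 to 216 with all 220 subjects). No visit or procedure is added. The change should be made before any unblinded look at d. The handling of d after closure and the repeated weekly tests need separate attention.

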7.1.2. Secondary Efficacy Assessments

Time to complete wound closure

The time (in days) from first treatment at baseline of the ulcer until it closes completely will be recorded.

Change in wound size over time

Ulcer size over time will be assessed from the digital photographs of the ulcer taken at each visit.

Incidence of recurrence

Recurrence is identified as an interruption in the epithelium following complete healing of the index ulcer. If the subject does have a recurrence, this will be documented and the re-opened ulcer will be measured and recorded

Incidence of Amputation

All amputations will be recorded. The investigator will judge whether the amputation was done because of the index ulcer or for different reasons.

Incidence of adverse events and device effects

Quality of Life

Pain - A Visual Analogue Scale will be used to determine pain levels.

Mood and Function - The Cardiff Wound Impact Schedule (CWIS) assesses levels of mood and function and is the tool used to determine Quality of Life (Appendix I). (Subjects in countries where the CWIS has not been validated will be debriefed on its use at the end of the study).

Economic Analysis

Economic assessments will be determined from the Euroqol-5D (EQ-5D), subject diary and

medical records documenting dressing changes, time, location and healthcare professional assistance and management (Appendix I).

Cost effectiveness will be determined by examining the difference in the number of healed ulcers in relation to the difference in cost in each randomized group

Incremental cost per additional ulcer healed=
$$\frac{\text{Cost of treatment (TWO) - Cost treatment (Control)}}{\text{Healed ulcers (TWO) - Healed ulcers (Control)}}$$

Cost Utility will be determined by examining the difference in Quality Adjusted Life Years (QALYs) associated with the different treatment regimens and their associated costs. Health utilities will be derived from the EQ-5D tool and used to calculate QALYs in each group. This will be related to overall treatment costs using the following formula

Incremental cost per QALY =
$$\frac{\text{Cost of treatment (TWO)-cost of treatment (control)}}{\text{QALY (TWO) - QALY(control)}}$$

See 7.2 Safety Endpoints

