Subjects whose index ulcers are confirmed as closed will enter into the follow-up phase and will be terminated from further treatment with TWO2 therapy or Control therapy. Subjects will be encouraged to continue to wear the standard off-loading boot/CROW boot during the follow-up phase.

8.2.8 12 Week Follow up

All subjects will be reviewed and followed up 12 weeks after “wound closure” or the 12-week “end of treatment phase”, whichever is sooner +/- 2 weeks. Data for 12 week follow up analysis will be collected per the subject’s preference by telephone or in the clinic if attending a routine visit for wound care. Index ulcers not yet healed, will continue to be treated with best available therapy as determined by the treating medical provider.

The following assessments will be performed on all subjects:

- 1) Verify Informed Consent
- 2) Record adverse events
- 3) Record changes in concomitant medication
- 4) Quality of Life Assessment using CWIS
- 5) Pain Assessment using the Visual Numerical Rating Scale (where possible, if applicable)
- 6) Digital Photograph of the open index ulcer
- 7) Health Economic Assessment (including EQ-5D)
- 8) Education on diabetes management (and foot care/off-loading when indicated)

8.2.9 38 Week Follow up

The 38 week follow up will take place 26 weeks +/- 2 weeks from the time of the last study visit (12 week follow up). Data for 38 week follow up analysis will be collected per the subject’s preference by telephone or in the clinic if attending a routine visit for wound care. Index ulcers not yet healed, will continue with best available therapy as determined by the treating medical provider.

- 1) Verify Informed Consent
- 2) Record adverse events
- 3) Record changes in concomitant medication
- 4) Quality of Life Assessment using CWIS
- 5) Pain Assessment using the Visual Numerical Rating Scale (where possible, if applicable)
- 6) Digital Photograph of the open index ulcer (where possible)
- 7) Health Economic Assessment (including EQ-5D)
- 8) Education on diabetes management (and foot care/off-loading when indicated)
- 9) Debriefing of subjects where CWIS not previously validated

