9 STATISTICAL ANALYSIS

9.1 Sample Size and Power Analysis

All sample size estimations in this section of the protocol were undertaken using the sampsi function in Stata 11 (Statcorp LP, Texas, USA). Comparisons of groups was made assuming no continuity correction.

Little data are available on similar studies using topical oxygen therapy within randomized clinical trials making sample size estimation problematic. Large trials of dermal substitutes and negative pressure have been undertaken that can be used to indicate the potential healing in the control group. The three large trials have control healing of between 18% and 28.9% around 12 weeks after entering the trial, with a mean of 28%.^{25,27,29}

The expected improvement in healing using the active device is more problematic as there have been few comparative studies published. Aburto and Frye undertook a randomized study of 20 venous ulcers and 20 diabetic foot ulcer patients.⁴² Topical oxygen demonstrated higher healing in the DFU patients after 90 days of 90% versus 40% in the control group. Blackman et al randomized 28 patients with DFUs and obtained a similar response (82.4% versus 45.5%).²² The potential difference between treatment groups was therefore 50% and 36.9% respectively. Using these studies a total sample size of 28 and 52 would be expected based on 80% power at the 5% level of significance. Neither of these studies was blinded. It is therefore likely that the effect is likely to be substantially smaller than that experienced in these two studies.

Because of the small size of these trials and lack of blinding it has been decided to offer a more cautious approach to the calculation of sample size based on a smaller expected benefit of oxygen therapy. By combining the results of the two randomized studies already undertaken the control group achieved a healing rate of 9/21 (42.8%). In the actively treated group healing occurred in 23/27 (85.2%). Assuming an expected control rate of 43% and a difference of half that experienced in these trials of 21% (to 64%) would require a sample size of 88 patients in each group (total=176), with a power of 80% and a level of significance set at $p<0.05$.

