9.2 General Statistical Methods

Analysis Populations

Two analysis populations will be evaluated: Intent To Treat (ITT) and Per Protocol (PP). The ITT population will be considered the primary population of interest and will include all subjects who were randomized to study treatment. The PP population will include all subjects who were randomized to study treatment and had no significant protocol violations that might affect the outcome of treatment.

All participants will be followed up to the primary end point (12 weeks) irrespective of whether they were on active treatment. Participants that withdraw from treatment continue to be followed up to the 12 week end-point. Participants that die, undergo amputation or who are lost to follow up will be considered as treatment failures.

Continuous demographic variables (age, ulcer duration, etc.) will be summarized for the study population as descriptive statistics (number, mean, median, SD, minimum and maximum value), and by randomized groups. No formal inferential statistical testing will take place of baseline values in relation to randomized groups.

Categorical demographic variables, such as gender, will be summarized as a proportion of the intention-to-treat population.

All analyses will be undertaken using the STATA 11 statistical package.

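### Section 9.4.3 gives the recurrence analysis no risk set or time origin, and neither available reading is a fair between-arm comparison; add a sustained-closure comparison among all randomized subjects

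*Combined protocol and SAP*

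**What the plan says.** - **Event (section 7.1.2).** "Recurrence is identified as an interruption in the epithelium following complete healing of the index ulcer". A subject whose index ulcer never heals cannot have the event.
- **Analysis (section 9.4.3).** "The wound recurrence rates will be analyzed with a time to event strategy as in 9.4.1". Nothing more is said about who is at risk, when the clock starts, or how never-healed subjects, death and amputation enter.
- **What 9.4.1 supplies.** A Cox model in which subjects who withdraw from treatment are "censored at the time they withdraw from the trial or are lost to follow up". On covariates: "Stepwise elimination of non significant covariates will be undertaken and only those covariates that remain statistically significant will be retained in the model". The candidate covariates are not named there.
- **Population (section 9.2).** "The ITT population will be considered the primary population of interest and will include all subjects who were randomized to study treatment". This is not tied to recurrence. The rule that death, amputation and loss count as failures is set out for the 12-week endpoint.
- **Missing data (section 9.5).** Subjects with missing data are left out of the relevant analysis.
- **Follow-up (sections 8.2.8 and 8.2.9).** There is a contact 12 weeks after closure or end of treatment and another 26 weeks later, each with a window of 2 weeks either way. Data are collected, as the subject prefers, "by telephone or in the clinic if attending a routine visit for wound care". The schedule in 8.1.1 lists photographs at both contacts but no wound assessment and measurement. Section 7.1.2 has a recurrence documented and the reopened ulcer measured, but does not ask for an onset date.

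**The concern.** Healing is the primary outcome, and the plan expects it to differ between arms by 21 points. If the device closes ulcers that would have stayed open on control, the healed group on TWO2 contains subjects with no counterpart among control healers. If those ulcers are also the ones more prone to reopen, the recurrence hazard ratio mixes any device effect on recurrence with the effect on who healed. A device with no effect on recurrence could then look somewhat worse.

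Putting all randomized subjects in the risk set does not cure this. Non-healers cannot recur, so the arm with more non-healers shows fewer recurrences.

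At stake is the interpretation of one secondary endpoint. No planned analysis reports how many of those randomized closed and stayed closed. The primary analysis is not affected.

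**Working it through.** **The plan's own figures.** Pooled-variance formula, two-sided, no continuity correction, p1 = 0.43, p2 = 0.64, mean 0.535:

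n = [z(α/2)·√(2·0.535·0.465) + 0.842·√(0.43·0.57 + 0.64·0.36)]² / 0.21²

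- α = 0.05 (z = 1.960): 87.4, so 88 per arm, as stated.
- α = 0.022 (z = 2.290): 109.3, so 110 per arm, as stated.

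The documents give no recurrence rate. Every recurrence figure below is an assumption.

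**Expected healers and events.** At 110 per arm, control healers = 110 × 0.43 = 47.3 and active healers = 110 × 0.64 = 70.4. At an assumed 30% recurrence in both arms, events are 14.2 and 21.1, about 35 in all.

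**Healer-only reading, no device effect on recurrence.** Let severity x be standard normal. The probability of healing is 1/(1 + exp(−(b − s·x))), with b set so that 43% and 64% heal. The cumulative recurrence hazard is λ·exp(g·x), with λ set so that 30% of control healers recur. Average over healers in each arm to get the recurrence risk R; then HR = ln(1 − R active) / ln(1 − R control).

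| s (healing, log-odds per SD) | g (recurrence, log-hazard per SD) | R control | R active | HR | Closed and recurrence-free, all randomized (active v control) |
|---|---|---|---|---|---|
| 0.7 or 1.5 | 0 | 30.0% | 30.0% | 1.00 | 44.8% v 30.1% |
| 0.7 | 0.4 | 30.0% | 31.3% | 1.05 | 44.0% v 30.1% |
| 1.5 | 0.7 | 30.0% | 33.9% | 1.16 | 42.3% v 30.1% |

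Last column: 0.64 × (1 − R active) v 0.43 × (1 − R control).

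**A coarser check.** Suppose everyone who heals on control would also heal on the device. Then 21/64 = 32.8% of active healers heal only because of it. If those subjects recur at 40% and the others at 20% (assumed), active recurrence is 0.672 × 20% + 0.328 × 40% = 26.6% v 20.0%, and HR = ln(0.734)/ln(0.800), about 1.38. With control recurrence of 10% to 40%, and 1.25 to 2 times that risk in device-only healers, the HR runs from 1.09 to 1.48. With equal risk it is 1.00.

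**All-randomized reading.** With 30% recurrence among healers in both arms, recurrence per randomized subject is 0.64 × 0.30 = 19.2% active v 0.43 × 0.30 = 12.9% control. The device looks worse only because it heals more.

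**Size against precision.** SE of log HR ≈ √(1/14.2 + 1/21.1) = 0.34. ln(1.05)/0.34 = 0.14 and ln(1.16)/0.34 = 0.44, so the bias is under half a standard error. The 95% interval multiplies or divides the HR by about exp(1.96 × 0.34) = 1.9.

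**Covariate adjustment.** In simulations of the severity model with s of 0 to 2 and g of 0 to 1, adjusting for true severity brought the HR back to about 1 (0.96 to 1.01). Complete measurement and adjustment would remove the bias.

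**Can the composite stand alone?** Suppose the device truly raises recurrence among healers to 45% against 30%: HR = ln(0.55)/ln(0.70) = 1.68. The composite is 0.64 × 0.55 = 35.2% v 30.1%, still in its favour. It shows no difference only when 0.64 × (1 − r) = 0.301, so r = 53% and the HR is about 2.1.

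**The case against.** The strongest reply is that 9.4.3 inherits a multivariable Cox model, so 1.05 to 1.16 is the bias with no adjustment and not the bias of the planned model. That stands as a limit on the size. It does not dispose of the point: 9.4.1 names no covariates, keeps only those that reach significance, and would be choosing among them on about 35 events. Severity that is not measured stays unadjusted.

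Second, the bias is small beside the sampling error, concerns one of seven secondary endpoints, and vanishes if severity does not drive recurrence. All of that stands.

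Third, durability among healed ulcers is a legitimate question, and a sustained-closure composite would answer a different one while hiding a real recurrence harm. This also stands, and it is why the composite should only be added.

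Fourth, carrying the failure rule of 9.2 to the last contact is a new choice. It would count a healed subject who misses a late call as not closed, while 9.5 would omit that subject. A sensitivity analysis is needed.

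A reader might infer more than the documents support:

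- **That the plan restricts the analysis to healers.** It does not say so; the restriction follows from the event definition on one reading.
- **That follow-up is mostly by telephone.** The text leaves this to the subject's preference and gives no frequency.
- **That recurrence dates must be treated as exact or cannot be known.** No onset date is required, but nothing prevents one being recorded.

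**Conclusion.** The point holds as a gap in specification with a modest, conditional bias. Section 9.4.3 leaves the risk set and time origin open. One reading compares groups selected after randomization; the other penalizes the arm that heals more.

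Under the severity model, with no device effect on recurrence, 43% v 64% healed and an assumed 30% recurrence in control healers, the unadjusted HR is about 1.05 to 1.16 against TWO2. Harsher assumptions in the coarser check give up to 1.48. It is 1.00 if severity does not drive recurrence. In the 1.05 to 1.16 scenarios, sustained closure among all randomized favours TWO2 by 12 to 14 points (42% to 44% v 30%), which no planned analysis would report.

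Two stronger conclusions are not supported. The documents do not show that the planned adjusted analysis will find the device harmful on recurrence: they give no recurrence rate and no link between severity and recurrence. Nor do they support dropping the healer-only comparison, since it can reveal a loss of durability that the composite would hide.

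**What to change.** Amend 9.4.3 in two parts.

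1. **Add an ITT comparison.** Compare the proportion of all randomized subjects closed by week 12 and recurrence-free at the 38-week contact. Count death, amputation and loss as failures, state that this extends the 9.2 rule and takes precedence over 9.5 for this outcome, and give a sensitivity analysis for missed late contacts.
2. **Keep the healer-only comparison and report it beside the composite.** Start time at confirmed closure. Replace stepwise selection with pre-specified baseline severity covariates, such as ulcer size and duration, which section 9.3 already considers. Use an interval-censored or discrete-time model where onset dates are not captured. State that this is not a randomized comparison.

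The cost is SAP wording; no new visits or data are needed. The downside is that the composite is dominated by the healing difference and can mask a recurrence harm, so the two results must be read together.
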